## **5.2 Subject Population Rationale**

This study will include adult subjects with a diagnosis of moderate to severe active ulcerative colitis eligible for use of anti-TNF- $\alpha$  therapy, i.e., subjects who had an inadequate response to conventional therapy including corticosteroids and 6-mercaptopurine (6-MP) or azathioprine (AZA), or who are intolerant to or have medical contraindications for such therapies.

Details about specific benefits and risks for subjects participating in this clinical trial may be found in the accompanying SmPC and Informed Consent documents.

## **5.3 Dose and Administration Rationale**

Golimumab will be used in this indication according to the SmPC.

## **5.4 Rationale for Future Biomedical Research**

Merck will conduct Future Biomedical Research on plasma specimens collected during this clinical trial. Such research is for biomarker testing to address emergent questions not described elsewhere in the protocol (as part of the main trial) and will only be conducted on specimens from appropriately consented subjects. The objective of collecting specimens for Future Biomedical Research is to explore and

identify biomarkers that inform the scientific understanding of diseases and/or their therapeutic treatments. The details of this Future Biomedical Research sub-trial are presented in Appendix 6: Collection and Management of Specimens for Future Biomedical Research. Additional informational material for institutional review boards/ethics committees (IRBs/ERCs) and investigational site staff is provided in Appendix 7.

## **6.0 TRIAL OBJECTIVES**

### **6.1 Primary Trial Objectives**

- To evaluate the correlation of serum soluble ST2 levels with endoscopic activity (endoscopic Mayo score) at week 6 in moderate to severe UC subjects under golimumab treatment.
- To evaluate the correlation of serum soluble ST2 with histological activity (Geboes index) at week 6 in moderate to severe UC subjects under golimumab treatment.

### **6.2 Secondary Trial Objective(s)**

- To evaluate the correlation of serum soluble ST2 levels with endoscopic activity (endoscopic Mayo score) at week 16 in moderate to severe UC subjects under golimumab treatment.
- To evaluate the correlation of serum soluble ST2 levels with histological activity (Geboes index) at week 16 in moderate to severe UC subjects under golimumab treatment.
- To correlate serum soluble ST2 levels with fecal calprotectin at week 6 and week 16 in moderate to severe UC subjects under golimumab treatment.
- To correlate serum soluble ST2 with clinical activity (total Mayo score) at week 6 and week 16 in moderate to severe UC subjects under golimumab treatment.
- To evaluate the potential of serum soluble ST2 as a predictor of endoscopic response (endoscopic Mayo score) to golimumab in moderate to severe UC subjects.
- To evaluate the correlation between serum soluble ST2 levels with maintenance of endoscopic response (endoscopic Mayo score) to golimumab.
- To correlate Mayo endoscopic score with UCEIS overall score at week 6 and week 16 in moderate to severe UC subjects under golimumab treatment.

### 6.3 Exploratory Objective(s)

- To evaluate the relationships of serum levels of golimumab and the presence of anti-golimumab antibodies with clinical, endoscopic, and histological activities and with biomarker levels in subjects with moderate to severe UC

## 7.0 INVESTIGATIONAL AND ANALYSIS PLAN

### 7.1 Overall Trial Design

This is an exploratory, multi-site, nonrandomized, open label, prospective, interventional, single-arm, study to evaluate the correlation of serum soluble ST2 levels with clinical, endoscopic and histological activity in subjects with moderate to severe active UC who received golimumab. During this study, golimumab will be used according to the SmPC.

The overall study design is illustrated in the trial design diagram presented in **Section 2.1**. Study procedures are outlined by visit in the trial flow chart in **Section 2.2**.

After signing the informed consent, subjects will enter a screening period of up to 42 days. After confirmation of eligibility criteria, subjects will initiate treatment with golimumab according to SmPC (Baseline Visit – V2). Subjects will be followed for a period of 16 weeks for clinical assessments and data collection. Biomarker samples (ST2 and fecal calprotectin) will be collected at baseline and at all subsequent visits. All subjects will be evaluated for clinical, endoscopic (fibrosigmoidoscopy) and histologic activity at screening, week 6 and week 16.

The trial design is appropriate for the indication studied. Validated methods of data collection, analysis, and evaluation will be used for the trial.

The method of assessment of serum soluble ST2 is described in **Section 7.6**.

In addition it will be evaluated the correlation between ST2 levels with fecal calprotectin, which is currently the best surrogate marker for the presence of intestinal inflammation. Fecal calprotectin has been demonstrated to be a sensitive and specific marker in identifying intestinal inflammation and response to treatment in subjects with IBD.

The Geboes index is a validated instrument for evaluating histologic disease activity in UC (Geboes et al., 2000) - see more detailed information in **Section 7.7.2.2**. This index will be applied at screening, week 6 and week 16 in order to determine if a correlation exists between its overall score and serum soluble ST2 levels at the respective time points.

Ulcerative Colitis Endoscopic Index of Severity (UCEIS) is a 3-item validated tool for assessing endoscopic severity of UC (Travis et al., 2011) - see more detailed information in **Section 7.7.2.2** and Appendix 4. This tool will be applied at screening, week 6 and week 16 in order to determine if a correlation exists between its overall score and the endoscopic Mayo score at the respective time points.

At this moment, little is known about the benefit of measuring golimumab serum concentrations in daily practice. In the pivotal PURSUIT Induction trial, an exposure-response relationship was observed for the change from baseline in Mayo score and rates of clinical response and clinical remission, with patients in the highest serum golimumab concentration quartiles having greater improvement in median Mayo scores and greater rates of clinical response and clinical remission when compared with those in the lower quartiles at week 6 (Sandborn et al., 2014a). A second study, also including UC patients from PURSUIT (Sandborn et al., 2016a and Sandborn et al., 2016b), assessed golimumab pharmacokinetics and exposure-response relationship. It was observed that serum golimumab concentrations are approximately dose proportional, and a positive serum golimumab concentration-efficacy relationship exists during induction/maintenance golimumab treatment of adult UC patients (Adedokun et al., 2016).

On the other hand, the presence of anti-drug antibodies may also be associated with low response to anti-TNFs since it is thought that anti-drug antibodies can neutralize the therapeutic antibodies or induce their rapid elimination (Vincent et al., 2013). To investigate these findings, comparisons of serum golimumab levels and the presence of anti-golimumab antibodies with clinical response and remission, endoscopic activity, fecal calprotectin and histological activity will be analysed as exploratory endpoints.

Serum golimumab levels and the presence of anti-golimumab antibodies will be evaluated at week 6 and week 16 using an ELISA (enzyme-linked immunosorbent assay) technique (IDKmonitor® Golimumab drug level ELISA and IDKmonitor® golimumab free ADA ELISA, from Immundiagnostik AG, Germany). These analyses will be done at the end of the study and will not be available to the investigators during subjects' participation in the study.

Considering these study aims, there is no justification for including a comparative arm.

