- 13 Stool culture and *Clostridium difficile* assay for toxin must be performed at screening or in the case of episode exacerbation as long as taken during the 4 months prior to inclusion.
- 14 The Subject Identification Card will be dispensed after the subject provides written informed consent and will be retrieved at the last visit.
- 15 Study medication will be dispensed at visit 2 and visit 3 for the following planned administrations. After study completion, and if physician finds it beneficial to the subject, golimumab will continue to be dispensed according to SmPC.
- 16 Prior to termination of study participation, all subjects should complete assessments indicated at Week 16 or Early Discontinuation.
- 17 Samples of ST2, calprotectin, and plasma for future biomedical research will only be collected at the Early Discontinuation visit in case the investigator discontinued the subject due to golimumab's lack of efficacy
- 18 Informed consent for plasma samples for future biomedical research must be obtained before the plasma samples are drawn. Plasma samples for analysis should be obtained pre-dose at Baseline/Day 1 and at Week 16 as the last sample drawn, on enrolled subjects only.
- 19 Golimumab levels and anti-golimumab antibodies will be measured in blood sample collected prior to study drug administration. Sample will be sent to a certified central laboratory for analysis.

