#### **7.4.1.1 Treatments Administered**

The first dose of subcutaneous (sc) golimumab will be administered at the trial site at Visit 2 (Day 1). Subsequent dosing will be done by the subject (i.e., unsupervised at his/her home) at week 2 and every 4 weeks thereafter (approximately the same time as the first administration), according to SmPC.

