#### **7.4.1.5.6 Dispensing**

The investigator or qualified designee(s) will dispense trial treatments at the designated site(s) to subjects who have provided written informed consent and have met the entry criteria. Clinical supplies may not be used for any purpose other than that which is stated in this protocol.

See the Trial Flow Chart in **Section 2.2** for a schedule of when clinical supplies are to be dispensed to the subjects. First administration of golimumab will be performed at the trial site during Baseline (V2), under supervision of the investigator or qualified designee(s). At this visit golimumab will be dispensed to the subject, for self-injection two weeks after the first administration. At week 6 (V3) golimumab will be dispensed in order to be administered at the day of this visit and at weeks 10 and 14, according to SmPC. Each subject will be instructed by the investigator or designee to return all unused and partially used investigational product to the site at week 6 (V3) and week 16 (V4). After study completion, and if physician finds it beneficial to the subject, golimumab will continue to be dispensed according to SmPC.

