#### 7.7.3.3 Exploratory endpoints

- To compare serum golimumab levels with clinical activity (total Mayo score) at weeks 6 and 16.
- To compare serum golimumab levels in subjects with endoscopic active disease (total Mayo score  $>2$ ) and subjects with inactive disease (total Mayo score  $\leq 2$  points with no individual subscore  $>1$ ) at week 6 and 16.
- To compare the presence of anti-golimumab antibodies (+ or -) and clinical activity (total Mayo score) at weeks 6 and 16.
- To compare the presence of anti-golimumab antibodies in subjects with endoscopic active disease (total Mayo score  $>2$ ) and subjects with inactive disease (total Mayo score  $\leq 2$  points with no individual subscore  $>1$ ) at week 6 and 16.
- To compare serum golimumab levels with endoscopic activity (endoscopic Mayo score) at weeks 6 and 16.
- To compare the presence of anti-golimumab antibodies (+ or -) and endoscopic activity (endoscopic Mayo score) at weeks 6 and 16.
- To compare serum golimumab levels with faecal calprotectin at weeks 6 and 16.
- To compare the presence of anti-golimumab antibodies (+ or -) and faecal calprotectin at weeks 6 and 16.
- To compare serum golimumab levels with histological activity (Geboes index) at weeks 6 and 16.
- To compare the presence of anti-golimumab antibodies (+ or -) and histological activity (Geboes index) at weeks 6 and 16.

- To compare quartile serum golimumab levels with rates of clinical response and clinical remission
- To compare serum golimumab levels between subjects who achieved response at week 6 and subjects who did not.
- To compare serum golimumab levels among subjects who achieved response at week 16 and subjects who did not.
- To compare the presence of anti-golimumab antibodies among subjects who achieved response at week 6 and subjects who did not.
- To compare the presence of anti-golimumab antibodies who achieved response at week 16 and subjects who did not.
- To compare serum golimumab levels between subjects who achieved remission at week 6 and subjects who did not.
- To compare serum golimumab levels among subjects who achieved remission at week 16 and subjects who did not.
- To compare the presence of anti-golimumab antibodies among subjects who achieved remission at week 6 and subjects who did not.
- To compare the presence of anti-golimumab antibodies who achieved remission at week 16 and subjects who did not.

See **Section 7.7.2.2** for the definitions of interest.

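### Antibody status comes from a free-antibody assay in on-treatment samples but is analysed as antibody presence, without reference to golimumab level

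*Combined protocol and SAP*

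**What the plan says.** **Assay.** Section 7.1 gives two commercial ELISA kits, one for golimumab level and one for antibodies. The antibody kit is described only by its product name, a "golimumab free ADA ELISA".

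**Timing.** The same section states: "Serum golimumab levels and the presence of anti-golimumab antibodies will be evaluated at week 6 and week 16". The flow chart (Section 2.2, footnote 19) adds: "Golimumab levels and anti-golimumab antibodies will be measured in blood sample collected prior to study drug administration". There is no baseline antibody sample. An early-discontinuation sample is listed, with no fixed interval from the last dose.

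**Dosing.** After the Day 1 dose, Section 7.4.1.1 has injections "at week 2 and every 4 weeks thereafter". Section 7.4.1.5.6 has the supply dispensed at week 6 "administered at the day of this visit and at weeks 10 and 14".

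**Endpoints and tests.** Section 7.7.3.3 codes antibody as a two-level variable, for example: "To compare the presence of anti-golimumab antibodies (+ or -) and endoscopic activity (endoscopic Mayo score) at weeks 6 and 16". Section 8.0 analyses these endpoints with two-group tests (t-test or Mann-Whitney) or, for categorical outcomes, chi-square or Fisher tests. Golimumab level is tested against the same outcomes in separate analyses.

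**Rationale.** Section 7.1 reports a positive relation between serum golimumab concentration and efficacy in earlier studies. It also says it is thought that "anti-drug antibodies can neutralize the therapeutic antibodies or induce their rapid elimination".

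**The concern.** An assay for free antibody need not measure the same thing as antibody presence. If antibody already bound to golimumab is not picked up, whether a subject tests positive depends on how much drug is in the sample as well as on whether antibody has formed. Section 7.1 also relates drug level to outcome. Drug level could then drive both the antibody reading and the outcome, and an unadjusted comparison of positives with negatives would mix an antibody effect with a drug-level effect.

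Two conclusions are at stake. The first is that a subject with a negative result has no antibodies. The second is that antibodies go with worse clinical, endoscopic or histological activity. As the analyses are written, a reader of the results would be led to both without being shown the drug level that qualifies them.

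**Working it through.** **The plan's own figure.** The documents give no figure for the antibody analyses. The only design figure concerns the ST2 correlation. Reading 0.75 as the true correlation, the Fisher z calculation is Φ[(atanh 0.75 − atanh 0.50) × √(37 − 3) − 1.645] = Φ(0.424 × 5.831 − 1.645) = Φ(0.825) = 0.795. This agrees with the stated 80%, and nothing in this point alters it.

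**Sample timing, from Sections 7.4.1.1, 7.4.1.5.6 and 2.2.** Doses fall at Day 1 and weeks 2, 6, 10 and 14.
- Week 6 sample: taken before that day's dose, 6 − 2 = 4 weeks after the last one, so at the end of a dosing interval.
- Week 16 sample: 16 − 14 = 2 weeks after the last dose, halfway through a four-week interval. No dose is due that day (the next on this schedule is week 18), so the pre-dose rule does not make it a trough sample.

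Both samples are on treatment. If detectability depends on drug level, it can differ between the two visits for that reason alone.

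**Number of comparisons, from Section 7.7.3.3.** Five antibody endpoints cover both visits: total Mayo score, active versus inactive disease, endoscopic score, calprotectin and histology. Four cover one visit each: response at weeks 6 and 16, and remission at weeks 6 and 16. That is 5 + 4 = 9 endpoints, or 5 × 2 + 4 = 14 comparisons.

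**What is not stated.** I find no drug tolerance for the kit, no step to separate antibody from drug before testing, no separate class for antibody-negative samples that contain drug, and no joint analysis of antibody with drug level.

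**Illustration of direction, on assumed values only.** Suppose true antibody status is unrelated to both drug level and outcome, and antibody reads positive only when drug is below a threshold t. Let drug level be standard normal and correlate with outcome at |r|. With true prevalence p, the drug level of apparent positives is lower by

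D = [φ(t)/Φ(t)] / [1 − p·Φ(t)],

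and their outcome is worse by |r| × D, in SD units. Take p = 0.10 to 0.30 and |r| = 0.3 to 0.5:

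| Share of samples above threshold | φ(t)/Φ(t) | D | Spurious outcome difference |
|---|---|---|---|
| 0% | 0 | 0 | 0 |
| 25% | 0.424 | 0.46 to 0.55 | 0.14 to 0.27 SD |
| 50% | 0.798 | 0.84 to 0.94 | 0.25 to 0.47 SD |
| 75% | 1.271 | 1.30 to 1.37 | 0.39 to 0.69 SD |

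For example, with 50% above the threshold and p = 0.20, D = 0.798 / (1 − 0.20 × 0.50) = 0.887. The difference is then 0.3 × 0.887 = 0.27 to 0.5 × 0.887 = 0.44 SD.

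This shows the direction of the artefact if masking occurs. It does not show that masking occurs in this trial, because masking is an input.

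**Cell sizes.** At the same assumed prevalences, 37 subjects would include 37 × 0.10 = 3.7 to 37 × 0.30 = 11.1 true positives, before any split by drug level.

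**The case against.** The strongest reply is that the documents say nothing about how the kit works beyond its name. That bound antibody reads negative is an inference from the word *free*. This stands: masking is possible, its extent is unknown, and the table above assumes it.

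Second, the protocol offers two mechanisms. If antibodies speed elimination of the drug, the drug level falls, masking lessens, and an association between positive status and low drug is a real consequence of antibody. Low drug would then lie on the path from antibody to poor response, and adjusting for it would remove part of the effect of interest. This also stands. The lack of a drug-level covariate is therefore not in itself an error; the gap is that the two measurements are never shown together.

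Third, the week 6 sample is taken when drug should be lowest within the dosing interval. That lessens the problem at week 6, but not at week 16.

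Fourth, these are exploratory endpoints in a study that calls itself exploratory, and the assay is openly named. That limits the weight of the point. It does not settle it, because the endpoint wording in Sections 6.3, 7.7.3.3 and 8.0 drops the word *free*.

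**Conclusion.** The point holds in a limited form. The plan reports a free-antibody result as antibody presence. Whether antibody is detected may depend on a drug level that the protocol itself relates to outcome, and that level is not brought into the antibody comparisons. A negative result with drug present does not establish absence of antibody. A poorer outcome among positives may partly reflect low golimumab, and partly a genuine effect of antibody on clearance. The comparisons as planned give no view of which.

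The size cannot be derived from the documents, which give neither drug tolerance nor prevalence. All nine antibody endpoints are touched; no primary or secondary ST2 analysis is.

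A reader might infer three stronger things that the documents do not support:
- That every subject with bound antibody will be misclassified, or that a given number of the 37 will be. Both the masking and the prevalence would have to be assumed.
- That the trial cannot address its antibody question. Golimumab level is measured at the same visits, so a joint presentation is possible without new data.
- That antibody-negative samples with measurable drug should be treated as not evaluable. All planned samples are on treatment, so this could remove most of the comparison group and would select subjects on the very variable at issue.

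**What to change.** In Sections 7.7.3.3 and 8.0:
1. Name the endpoint *free anti-golimumab antibodies*, and limit conclusions to free antibody.
2. Beside each outcome comparison, report antibody status jointly with the same-visit golimumab level (by level or by detectability). Show antibody-negative with drug present as its own category; do not exclude it.
3. State that antibody status at week 6 and at week 16 is not to be read as comparable, because one sample is at trough and the other mid-interval.

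In Section 7.1, state the assay's drug tolerance as obtained from the manufacturer or the central laboratory.

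The cost is wording and a set of tables from data already planned. The drawback is small cells at 37 subjects, so the joint tables should be labelled descriptive.

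A drug-tolerant assay on stored serum is an option, since Section 7.1 has these assays run at the end of the study. It depends on a suitable method and enough remaining sample, neither of which the documents show.

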## 7.2 Beginning and End of the Trial

Each subject is considered to be enrolled in the trial when he/she (or the subject's legal representative) has provided written informed consent.

Each subject is considered to have ended participation in the trial when he/she has completed the last protocol-specified contact (e.g., visits or telephone contacts) or prematurely discontinues from the trial.

A subject is considered to have discontinued after he/she has withdrawn consent or has been discontinued under the conditions specified in **Section 7.3.3**.

A subject is considered to have been lost to follow-up if he/she is unable to be contacted by the investigator. The end of participation for a subject lost to follow-up is the last known contact (e.g., visit or telephone contact).

Subjects may be rescreened one time only, and only for the reason of initially failing to meet the Visit 1 inclusion/exclusion criteria related with the severity of the disease.

The overall trial begins when the first subject is enrolled (i.e., signs the informed consent form). The overall trial ends when the last remaining subject has ended participation in the trial, by completing the trial, being discontinued from the trial, or being lost to follow-up.

Each subject will be monitored for the occurrence of AEs immediately after he/she has signed informed consent and until the last protocol-specified visit. Follow-up procedures related to pregnancy or SAEs may continue beyond the end of the clinical trial.

Each subject will participate in the trial for approximately 22 weeks from the time the subject signs the Informed Consent Form (ICF) until the final protocol-specified contact. After a screening phase of up to 6 weeks each subject will receive golimumab (**Section 7.4.1.1**) for 16 weeks.

